## 3.2 Efficacy Variables

### 3.2.1 Primary Efficacy Variable

The primary efficacy variable is difference (improvement) on plasma thromboelastographic MCF from baseline to 1-hour post-infusion. ROTEM measures will be performed at the central laboratory of the study.

### 3.2.2 Secondary Efficacy Variables

Secondary efficacy variables assessed in this study are:

1. Difference (improvement) on other plasma thromboelastographic variables (clotting time [CT], clot formation time [CFT], and alpha angle [ $\alpha$ ]) from baseline to 1-hour post-infusion. ROTEM measures will be performed at the central laboratory of the study.
2. Difference (improvement) on standard coagulation tests (thrombin time [TT], prothrombin time [PT], and activated partial thromboplastin time [aPTT]) from baseline to 1-hour post-infusion. Standard coagulation tests will be performed at the central laboratory of the study.

### 3.3 Safety Variables

The following safety variables will be assessed in this study:

1. AEs
2. Vital signs
3. Physical assessments
4. Laboratory panels
5. Antibodies against fibrinogen (immunogenicity testing)
6. Allergic/hypersensitivity reaction
7. Thrombotic event
8. Viral safety

## 4 GENERAL STATISTICAL CONSIDERATIONS

Statistical analyses and data presentations will be generated using SAS version 9.4 or higher.

Unless otherwise noted, for continuous variables, descriptive statistics will include the number of non-missing values, mean, standard deviation (SD), median, minimum and maximum. For categorical variables, descriptive statistics will include counts and percentages per category. All statistical inference will be tested at 2-sided with  $\alpha=0.05$ .

Unless otherwise noted, all data collected in the electronic case report forms (eCRFs) or electronically transferred (such as central laboratory data) will be presented in data listings. Subjects will be identified in the data listings by subject number (which includes site number) and grouped by adult and pediatric populations.

For table summaries, the data will be presented at the scheduled visits according to protocol. Any data collected at the unscheduled visits will be listed.

### 4.1 Data Handling

Unless otherwise noted, if an observation is missing at a specific scheduled visit/timepoint, the value at that visit will not be imputed and will be set to missing.

Baseline will be defined as the last measurement taken prior to the start of the infusion on Day 0 (Infusion Visit).

#### 4.1.1 PK Data Handling

##### 4.1.1.1 Time Window for Pharmacokinetic Analysis

The scheduled time points specified in the protocol will be used in the tables for presenting the individual and summary data of plasma fibrinogen concentrations. The nominal time (hours post start of infusion) will be used in figures for presenting the mean or median measured concentration vs. time curve. Due to the variable infusion durations in individual subjects and the considerable difference of mean infusion durations between the adult and pediatric groups, the nominal time will be adjusted by using the mean infusion duration of 1 hour and 0.5 hour for the adult and pediatric groups, respectively.

If PK blood samples are not drawn exactly at the protocol specified time, the samples will still be included in the PK analysis as long as the actual sample collection date and clock time for each sample is recorded and the actual elapsed time from the start of infusion can be calculated.

The actual elapsed time between the start of the infusion and each PK blood sample draw will be calculated and used as the PK time point. In addition, the actual duration of the infusion will be calculated to determine the time of the end of infusion. The PK parameter calculation for each subject will be based on the actual elapsed time from the start of infusion instead of the scheduled time or nominal time post end of infusion.

An example of actual elapsed time calculated from the time of the start of infusion is shown below.

Scheduled Time	Nominal Time (Hours post SOI) for Adult	Nominal Time (Hours post SOI) for Pediatric	Example Actual Elapsed Time (Hours post SOI)
Pre-infusion	**	**	**
Start of infusion	0	0	0
End of infusion*	1	0.5	1.25
30 minutes post-infusion	1.5	1	1.75
1 hour post-infusion	2	1.5	2.20
2 hours post-infusion	3	2.5	3.35
4 hours post-infusion	5	4.5	5.30
8 hours post-infusion	9	8.5	9.56
Day 1 (24 hours post-infusion)	25	24.5	25.90
Day 2 (48 hours post-infusion)	49	48.5	49.80
Day 4 (96 hours post-infusion)	97	96.5	97.67
Day 6 (144 hours post-infusion)	145	144.5	145.50

Day 9 (216 hours post-infusion)	217	216.5	217.75
Day 14 (336 hours post-infusion)	337	336.5	337.20

\*End of infusion is not a defined time point in order to facilitate the different infusion times required per patient and serves as a relative measure for the calculation of nominal times of the post-infusion time points.

SOI – Start of infusion

\*\*The pre-infusion concentration will be used for the baseline concentration regardless of actual time taken so long as it occurs before the SOI.

#### **4.1.1.2 Plasma Concentration Values Below the Quantification Limit**

If any plasma concentration values of fibrinogen are below the lower limit of quantification (LLOQ) for either the activity (Clauss) method or the antigen (ELISA) method, in general the values will be replaced with a value of zero for the PK analysis. If necessary, alternative methods may be used to impute the values below LLOQ based on PK principle, and such methods will be documented in the CSR.

#### **4.1.1.3 Plasma Concentration Missing Values**

For PK analysis, any invalid plasma concentration values of fibrinogen will be treated as missing. If necessary, invalid or missing values will be interpolated or extrapolated using PK principle, as appropriate, and such interpolations or extrapolations will be documented in the CSR.

#### **4.1.2 Efficacy Data Handling**

For the ROTEM measurements, undetectable values of MCF and alpha angle are set to 0, and undetectable values of CFT and CT are set to missing.

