7.2 METHODS AND TIMING FOR ASSESSING, RECORDING, AND ANALYSING OF EFFICACY PARAMETERS

7.2.1 CHANGE ON MAXIMUM CLOT FIRMNESS (MCF) MEASURED BY ROTATIONAL THROMBOESLATOGRAPHY (ROTEM)

The primary efficacy endpoint will be the mean change on MCF from baseline to 1 hour after the end of the infusion.

All rotational thromboelastographic measures on frozen plasma samples will be analyzed at a central laboratory using ROTEM, Pentapharm GmbH, Munich, Germany).

MCF is a functional parameter indicative of blood's ability to clot and is mainly dependent on platelet concentration and functionality and fibrinogen concentration and activity. On frozen plasma samples, where platelet function is considered to be abolished, MCF will be almost exclusively dependent on fibrinogen concentration and functionality, thus providing a surrogate measure of hemostatic efficacy of the study drug.

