9.1.3.2 Analysis of secondary efficacy endpoints

Secondary study variables will be examined in the evaluable and PP populations.

1. Mean change on other thromboelastographic variables:

Mean change (difference) in thromboelastographic variables: CT, CFT, and α in plasma samples pre-infusion and 1-hour post-infusion will be analyzed.

Similar analyses to those performed on the primary efficacy endpoint will be run on secondary efficacy endpoints.

2. Mean change on standard coagulation tests:

Mean difference in standard coagulation tests: TT, PT, and aPTT in plasma samples pre-infusion and 1-hour post-infusion will be analyzed.

Similar analyses to those performed on the primary efficacy endpoint will be run on secondary efficacy endpoints.

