9.5 PROCEDURES FOR ACCOUNTING FOR MISSING, UNUSED, AND SPURIOUS DATA

For the PK analysis, any missing or not valid values for fibrinogen concentration will be treated as missing, or if necessary, will be interpolated or extrapolated using PK principle, as appropriate, and will be documented in the clinical study report.

For primary efficacy endpoint analysis, the missing value in change from baseline in MCF will be set to zero.

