### **Evaluable population (efficacy)**

The Evaluable population will include all subjects who received IP at any amount and who have at least two measurements for the primary efficacy variable: one pre-infusion MCF and 1-hour post-infusion MCF measurements by ROTEM.

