### 10.2 Secondary Efficacy Analyses

Secondary efficacy analyses will be performed in the Evaluable and PP populations. Secondary efficacy variables including change (difference) in other thromboelastographic variables (CT, CFT,  $\alpha$ ) and standard coagulation tests (TT, PT, aPTT) in plasma samples pre-

infusion and 1-hour post-infusion will be summarized by adult and pediatric populations and overall.

Statistical analyses using the one sample t-test for paired observations and the Wilcoxon signed rank test will be performed on the secondary efficacy endpoints, similar to the analyses on the primary efficacy endpoint.

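### Undetectable CT and CFT are set to missing, so both tests use only pairs measurable at both times and a change to or from undetectable cannot count

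*SAP*

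**What the plan says.** SAP 4.1.2 treats undetectable ROTEM results in two ways: "undetectable values of MCF and alpha angle are set to 0, and undetectable values of CFT and CT are set to missing". SAP 4.1 adds that for a missing observation, unless otherwise noted, "the value at that visit will not be imputed and will be set to missing". Nothing is noted for CT or CFT.

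SAP 10.2 then says: "Statistical analyses using the one sample t-test for paired observations and the Wilcoxon signed rank test will be performed on the secondary efficacy endpoints". Protocol 9.1.3.2 agrees: "Similar analyses to those performed on the primary efficacy endpoint will be run on secondary efficacy endpoints". The endpoint is the change from baseline to 1 hour after the infusion.

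On the analysis set, SAP 10.2 states: "Secondary efficacy analyses will be performed in the Evaluable and PP populations". The Evaluable population (SAP 4.2) consists of treated subjects "who have at least two measurements for the primary efficacy variable: one pre-infusion MCF and 1-hour post-infusion MCF measurements by ROTEM". Membership thus depends on MCF alone.

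The only readable rule that fills in a missing efficacy value is in Protocol 9.5, and it is confined to the primary endpoint: "the missing value in change from baseline in MCF will be set to zero".

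**The concern.** An undetectable CT or CFT from a completed ROTEM run is a known result: no clot signal was registered. Coding it as missing puts it with samples that were never drawn or analysed. Three consequences follow.

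- A subject who goes from undetectable to measurable (a response), or from measurable to undetectable (a worsening), is removed because of the outcome.
- The CT and CFT tests carry the Evaluable label but cover only subjects measurable at both times. The same blood sample can count for MCF and alpha angle, at 0, and be absent for CT and CFT.
- Protocol 7.2.2 expects treatment to improve CT and CFT, yet the clearest form of improvement cannot register in either test.

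Undetectable baselines are plausible. Protocol 5.1 admits only subjects whose fibrinogen is undetectable or no higher than 30 mg/dL, and Protocol 7.2.1 says: "On frozen plasma samples, where platelet function is considered to be abolished, MCF will be almost exclusively dependent on fibrinogen concentration and functionality". That sentence concerns firmness, so applying it to CT and CFT is an inference.

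**Working it through.** **Does any rule restore the pairs?** An undetectable value becomes missing (SAP 4.1.2), is not imputed (SAP 4.1), and so gives no change for a paired test (SAP 10.2). Protocol 9.5 covers MCF only. The Evaluable definition does not require a CT or CFT pair. No readable text provides a responder count, shift table, worst-rank analysis or censored-value analysis for CT or CFT. The pairs are lost.

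**Inputs.**
- Ten evaluable adults and ten evaluable pediatric subjects (SAP 2.1 and 4.3), so N = 20 overall and 10 per cohort.
- Two-sided alpha 0.05 (SAP 4).
- The documents give no sample size, effect size or power for CT or CFT, so there is no planned figure to reproduce.
- The share measurable at baseline (p0) and the share of those also measurable at 1 hour (p1) are not stated. The values below are assumptions.
- SAP 10.2 does not say whether the Wilcoxon test is exact. Exact is assumed.

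**Pairs needed for the Wilcoxon test.** The smallest exact two-sided p with n pairs is 2/2^n: 0.25 for n = 3, 0.125 for n = 4, 0.0625 for n = 5 and 0.031 for n = 6. At least 6 pairs are needed for p<0.05.

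**Chance of at least 6 pairs** = 1 − BinomCDF(5; N, p0 × p1):

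| N | p1 | p0 = 20% | p0 = 30% | p0 = 50% |
|---|---|---|---|---|
| 20 | 100% | 20% | 58% | 98% |
| 20 | 90% | 14% | 46% | 94% |
| 20 | 80% | 9% | 34% | 87% |
| 10 | 100% | 0.6% | 5% | 38% |
| 10 | 90% | 0.4% | 3% | 26% |
| 10 | 80% | 0.2% | 2% | 17% |

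**The t-test.** It has no 6-pair floor, but it uses the same selected pairs. At an assumed standardized change of 1.0, noncentral-t power is 99%, 96%, 88%, 68% and 29% with 20, 16, 12, 8 and 4 pairs. Those counts correspond to 0%, 20%, 40%, 60% and 80% of 20 subjects being undetectable at baseline, with everyone measurable at 1 hour. If all are undetectable at baseline, neither test can be run.

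**Constructed examples, 20 subjects each.**
- (a) Sixteen go from undetectable to measurable, and four measurable pairs all improve. The plan has 4 pairs, and its smallest exact Wilcoxon p is 0.125. With 4 pairs the t-test reaches p<0.05 only if mean/SD exceeds 3.182/√4 = 1.59. A sign test in all 20 gives 20 of 20, p = 2/2^20 = 0.000002.
- (b) Six measurable pairs improve, six go from measurable to undetectable, and eight are undetectable twice. The plan sees 6 of 6, Wilcoxon p = 0.031 in favour. A sign test without ties gives 6 against 6, p = 1.0; 6/20 = 30% improved, exact 95% CI 12% to 54%.

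**Validity of a sign test that excludes ties.** With no true effect and tie shares of 0, 10%, 20%, 30% and 50%, its exact type 1 error is 0.041, 0.032, 0.030, 0.026 and 0.023 for N = 20, and 0.021, 0.025, 0.021, 0.018 and 0.009 for N = 10. It stays below 0.05 throughout.

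**The case against.** A clotting time with no finite value cannot enter a mean, so the rule is reasonable for the mean change that the protocol specifies. That stands, and it is why the existing analysis should be kept. It does not justify leaving the direction of change, which is known, out of every test.

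The 6-pair floor concerns the Wilcoxon test only, and the t-test is named first. With 4 pairs the t-test still has 75% power at an assumed standardized change of 2. This limits what the table shows, but not the selection, which both tests share.

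Example (b) is unlikely. Protocol 2.4 considers the dose sufficient to reach at least 1 g/L, and Protocol 7.2.2 expects improvement, so the likelier loss is of responders, which understates the effect. That is fair: (b) shows only that the rule can err in the other direction.

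The share undetectable is unknown, and with few such readings the loss is small. Also correct.

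Much of the information survives elsewhere. MCF and alpha angle keep these subjects at 0, SAP 10 reports the non-missing n, and the data are listed. The loss would be visible, but neither test would reflect it. Protocol 7.2.2 assigns CT to the initiation phase, which MCF and alpha angle do not replace. Parts of SAP 10 and 10.1 are blacked out, so further handling there cannot be ruled out, although the readable SAP 10.2 governs CT and CFT.

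**Conclusion.** The concern holds. The written rules remove known CT and CFT results from both tests because of what those results are, and the Evaluable label does not describe the subjects tested. How much is lost depends on the unstated share of undetectable readings. Under the assumed shares, the chance that an exact Wilcoxon test could reach p<0.05 at all ranges from 9% to 98% in 20 subjects and from 0.2% to 38% in a cohort of 10. The direction of bias is not fixed by the documents, though loss of responders is the more likely case.

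Severity is minor. Two of six secondary variables are affected, no readable success criterion rests on them, the sample size is based on PK, and the primary endpoint is unaffected.

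**What to change.** 1. SAP 4.1.2: record an undetectable CT or CFT from a completed ROTEM run as undetectable, ranked worse than any measured value. Reserve missing for samples not drawn or not analysed.
2. SAP 10.2: keep the mean change, paired t-test and Wilcoxon test, labelled as measurable pairs only, with n shown.
3. SAP 10.2: for CT and CFT separately, add an exact two-sided sign test in all Evaluable subjects with both ROTEM runs. Undetectable to measurable, or a shorter measured time, is improved; measurable to undetectable, or a longer measured time, is worsened. Ties (undetectable twice, or equal measured values) are left out of the test and their number is reported. State the test's role beside the two existing tests, and whether it is repeated in the adult, pediatric and PP sets.
4. Add a table of detectable against undetectable, baseline by 1 hour, and the proportion improved among all such subjects with an exact 95% CI, as a descriptive figure not tested against 50%.
5. List the change in SAP Section 12.

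The cost is wording in three SAP sections plus one test and one table per variable, with no new data and the protocol's mean-change analysis intact. The drawbacks are a further test per variable, no use of the size of change, and low power when few subjects change (5 of 5 gives p = 0.0625).

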### **4.2 Analysis Populations**

#### **Safety population**

The Safety population consists of all subjects who receive infusion (at any dose) of the IP. This will be the analysis population for the safety data.

#### **PK population**

The PK population will consist of all subjects who have received study medication and have sufficient fibrinogen plasma concentration data to facilitate calculation of PK parameters. The PK population will be used for the analyses of the PK parameters.

Adequate treatment compliance will be considered when determining valid concentration-time data for inclusion in the PK analyses. The values or profiles deemed not reliable due to treatment non-compliance or other reasons will be excluded from the PK analyses and flagged in the listing. Any subject who has at least one major protocol deviation which might

have impact on the PK analyses (to be defined in a data review meeting prior to database lock) will be excluded from the PK population.

### **Evaluable population (efficacy)**

The Evaluable population will include all subjects who received IP at any amount and who have at least two measurements for the primary efficacy variable: one pre-infusion MCF and 1-hour post-infusion MCF measurements by ROTEM.

### **Per-protocol population (efficacy)**

The Per-protocol (PP) population will include all subjects who received planned dose of the IP (at least 90% of the planned dose based on the prepared volume), who have no major protocol violation that might have impact on the primary efficacy assessment (to be defined in a data review meeting prior to database lock), and who have at least two measurements for the primary efficacy variable: one baseline (pre-infusion) MCF measurement by ROTEM and 1-hour post-infusion MCF measurement by ROTEM for the investigational medicinal product.

Any deviations from the protocol will be recorded in the protocol deviation list. The validity of a subject for inclusion in each of these four populations (Safety, PK, Evaluable, and PP) will be assessed at a data review meeting that will take place before database lock. The data review meeting will review the protocol deviation list, as well as data listings. If additional protocol deviations are identified which justify removing a subject from any population, then these decisions will be documented.

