9.7.3 POPULATION FOR STATISTICAL ANALYSIS OF SAFETY

All subjects who receive infusion (at any dose) of the investigational product will be included in the safety population.

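### SAP 4.2 lets a pre-lock data review meeting remove a subject from the Safety or Evaluable population for a protocol deviation, although neither set has a deviation criterion

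*SAP*

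**What the plan says.** On Safety, SAP 4.2 states: "The Safety population consists of all subjects who receive infusion (at any dose) of the IP". Protocol 9.7.3 agrees: "All subjects who receive infusion (at any dose) of the investigational product will be included in the safety population". On Evaluable, SAP 4.2 states: "The Evaluable population will include all subjects who received IP at any amount and who have at least two measurements" of the primary variable, one before the infusion and one an hour after it. Protocol 9.7.2 defines the set in the same way. None of these definitions mentions protocol deviations.

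The SAP's PK and PP definitions do. A major deviation that could affect the PK analyses takes a subject out of PK, and one that could affect the primary efficacy assessment takes a subject out of PP. In both cases the data review meeting is to settle what counts.

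The closing paragraph of SAP 4.2, printed under the PP heading, goes further: "The validity of a subject for inclusion in each of these four populations (Safety, PK, Evaluable, and PP) will be assessed at a data". The rest of that sentence places the assessment in the review meeting, ahead of database lock. On the material used: "The data review meeting will review the protocol deviation list, as well as data listings". It ends: "If additional protocol deviations are identified which justify removing a subject from any population, then these decisions will be documented".

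SAP 10 runs the efficacy analyses on Evaluable and treats PP as a sensitivity analysis. SAP 11 bases the safety analyses on Safety. Among the population definitions in Protocol 9.7, the meeting has one task, defining major violations for PP. SAP 12, which records departures from the protocol, mentions no wider task.

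**The concern.** On a plain reading, the definitions and the closing paragraph cannot both stand. PK and PP already carry their own deviation rules, so the closing sentence adds little for them. What it adds is authority over Safety and Evaluable. For those two sets it gives no criterion beyond the deviation being thought to justify removal, and no control beyond documentation and timing before lock.

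Timing protects less here than in a blinded trial. Protocol 4.4.2 states that the study is open-label. SAP 4 provides that, unless otherwise noted, eCRF data and data "electronically transferred (such as central laboratory data) will be presented in data listings". For the primary variable, SAP 3.2.1 says "ROTEM measures will be performed at the central laboratory of the study", so MCF falls within the listings, and SAP 11.1 lists all AEs. Nothing withholds either from the meeting. SAP 12 also shows that fibrinogen levels had been looked at before the SAP was amended, and SAP 4.4 permits PK and efficacy interim analyses in adults.

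Two things are at stake: a safety denominator that counts everyone exposed, and a primary efficacy set that stays distinct from the per-protocol set.

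**Working it through.** **The plan's own figure.** SAP 4.3 and Protocol 9.2 give 11 enrolled per age group for 10 evaluable. With the stated 10% dropout, 10 × 1.10 = 11, which reproduces it. (Dividing instead gives 10/0.90 = 11.1, or 12 rounded up; the difference does not matter here.) Two groups give 11 + 11 = 22 enrolled and 10 + 10 = 20 evaluable. No power, effect size or SD for the MCF change is stated, so there is no power figure to reproduce.

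**Texts side by side.**

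| Population | Deviation criterion, SAP 4.2 definition | Deviation criterion, Protocol 9.7 | Covered by closing paragraph of SAP 4.2 |
|---|---|---|---|
| Safety | none | none | yes |
| Evaluable | none | none | yes |
| PK | major deviation affecting PK | none | yes |
| PP | major violation affecting primary efficacy | major violation | yes |

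The conflict is in the first two rows.

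**Safety rates.** Assume that every enrolled subject is dosed, that one has the event of interest, and that this subject is removed. Exact (Clopper-Pearson) 95% limits for x events in n are: lower, the 2.5% point of Beta(x, n − x + 1); upper, the 97.5% point of Beta(x + 1, n − x). For x = 0 the upper limit is 1 − 0.025^(1/n).

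- Overall, kept: 1/22 = 4.5% (0.1 to 22.8%). Removed: 0/21 = 0%, upper limit 1 − 0.025^(1/21) = 16.1%.
- Adults, kept: 1/11 = 9.1% (0.2 to 41.3%). Removed: 0/10 = 0%, upper limit 1 − 0.025^(1/10) = 30.8%.

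**Estimated MCF change.** Assume n Evaluable subjects, one with zero change and the others with mean m. The mean with everyone kept is (n − 1)m/n; with that subject removed it is m. The ratio is n/(n − 1).

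- n = 20: 20/19 = 1.053, a rise of 5.3%.
- n = 10 (one age group): 10/9 = 1.111, a rise of 11.1%.

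**Primary test.** Let r be mean/SD of the change in the other n − 1 subjects. The documents do not give r, so 0.4 to 3 is an assumed range. With the subject removed, t = r√(n − 1) on n − 2 df. With the subject kept, in units of that SD, the mean is (n − 1)r/n and the sum of squares is (n − 2) + (n − 1)r²/n, on n − 1 df. Two-sided p-values:

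| r | n = 20, kept | n = 20, removed | n = 10, kept | n = 10, removed |
|---|---|---|---|---|
| 0.4 | 0.098 | 0.098 | 0.262 | 0.264 |
| 0.5 | 0.043 | 0.043 | 0.171 | 0.172 |
| 1 | 0.0004 | 0.0004 | 0.019 | 0.017 |
| 2 | <0.0001 | <0.0001 | 0.0007 | 0.0003 |
| 3 | <0.0001 | <0.0001 | 0.0001 | <0.0001 |

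At every ratio tried, p stays on the same side of 0.05.

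**The case against.** The closing sentence is conditional. It speaks of deviations that justify removal, and since Safety has no deviation criterion, one could say that none ever does; the meeting would then only check each subject against each definition. This reading is possible but strained, because the paragraph names Safety and Evaluable and extends to any population. If it is what the sponsor means, saying so costs nothing.

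Review of Evaluable also has a proper use. Membership needs a usable 1-hour MCF. Protocol 4.6.2 allows ±10 minutes for that sample, and Protocol 6.2 disregards efficacy results from the time another fibrinogen-containing product is given. A subject given one before the 1-hour sample would lose that value and so leave the set. This stands, and a flat ban on any change to Evaluable would be wrong.

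A reader might infer that a removed subject and the subject's AEs could vanish from the report. The documents do not support that. The protocol's summary of the safety analysis has AEs of every infused subject listed in the clinical report, and SAP 11.1 lists all AEs. Protocol 9.1.4 has thrombotic events evaluated individually, Protocol 8.3.7 sends them to the sponsor on the SAE form whether or not serious, and under Protocol 8.2.7 one confirmed case suspends enrollment and dosing. None of this depends on population membership. SAP 5 reports the number in each population, SAP 6 summarizes deviations, and removals are documented. A summary rate could change, but not invisibly.

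That the meeting will know the outcomes is an inference: the SAP says only that it sees data listings. With a single arm, selection between arms cannot arise.

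**Conclusion.** The concern holds at moderate severity. The closing paragraph of SAP 4.2 permits removals that the Safety and Evaluable definitions, and Protocol 9.7.2 and 9.7.3, do not. It sets no criteria for them, in a trial where nothing hides results from the meeting. SAP 12 does not declare the wider role. One caveat applies: SAP 1 names Protocol Version 2.3 as its basis, the protocol at hand is Version 3.0, and the wording of Version 2.3 cannot be checked.

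The exposure is limited to summary safety rates and denominators and to the estimated MCF change. The safety figures assume that all 22 are dosed and that the one subject with the event also has a deviation the meeting treats as grounds for removal. The 5.3% shift assumes 20 Evaluable subjects and a removed subject with zero change. On those terms the primary test's conclusion is unlikely to change, though the MCF mean/SD ratio is assumed and a removed subject with a different value would give different figures.

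A reader might also infer that the primary analysis becomes a second per-protocol analysis picked after the results are seen. The SAP does not say that. PP keeps its own conditions, including at least 90% of the planned dose, and nothing directs the meeting to apply them to Evaluable. The fault is an open permission, not a planned selection.

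**What to change.** Reword the closing paragraph of SAP 4.2 to say:

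- Protocol deviations can remove a subject only from the PK and PP populations.
- Safety membership depends only on having been infused.
- Evaluable membership depends only on any infusion plus a valid pre-infusion and a valid 1-hour MCF. A value may be set aside only under rules fixed beforehand, such as Protocol 6.2 on other fibrinogen-containing products, and not by judgement at the meeting. If samples outside the 1-hour window are to be treated as invalid, that rule should be written into the SAP as well.

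The meeting can still check each subject against these definitions. The change should be made before the meeting is held, because a later removal could not be told apart from one prompted by the results. It costs a few sentences in one paragraph of the SAP and needs no new data, subjects or procedures.
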